3.2. Discussion of Study Design

Overall

Data from in vitro studies with cloned expressed CYP enzymes and human liver microsomes indicate that CYP3A4 is the primary enzyme that metabolizes LOXO-305. Furthermore, LOXO-305 is a substrate for P-gp, thus rendering LOXO-305 susceptible to DDI when co-administered with inhibitors or inducers of CYP3A4 and/or P-gp.

The fixed single-sequence design used in this study is typical for interaction studies where a relatively small number of subjects are required, because it allows intra-subject comparisons. This study will be open-label because the study endpoints are not considered subjective.

Multiple doses of itraconazole and rifampin will allow the DDI effect(s) of both study drugs on LOXO-305 to be assessed at steady-state, therefore the maximal inhibition or induction effect on CYP3A4 and P-gp will be achieved.

Conducting the study in healthy adult subjects mitigates the potential confounding effects of the disease state and concomitant medications.

Part 1 – Itraconazole (CYP3A4 and P-gp Inhibitor)

In Part 1, the effects of multiple oral doses of itraconazole (a strong CYP3A4 and P-gp inhibitor) on the PK of LOXO-305 will be investigated. Itraconazole is a well-characterized, competitive, strong inhibitor of CYP3A4 and a potent inhibitor of P-gp; thus it was selected for this study as per recommendations in the Food and Drug Administration (FDA) Guidance for Drug Interaction Studies.⁶ Itraconazole capsules, when administered alone (ie, Days 8

to 11, and Days 13 to 18), will be administered under fed conditions (ie, approximately 30 minutes after the start of a standard meal [breakfast or evening meal]) to enhance oral absorption and ensure that adequate plasma concentrations are attained for maximal inhibitory effect on CYP3A4 at steady-state. When co-administered with LOXO-305; however, both drugs will be administered in the fasted state, as the effect of food on the PK of LOXO-305 has not yet been fully evaluated. As this will be the first time LOXO-305 will be administered with a CYP3A4 inhibitor in healthy adult males and females of non-childbearing potential, Part 1 will include a sentinel cohort for safety purposes. This sentinel cohort will comprise 3 subjects. Following completion of the sentinel cohort, the Investigator and Sponsor will review all pertinent safety and tolerability data (and PK data, if available) from the sentinel cohort before proceeding to dose the remaining 9 subjects in the second cohort in Part 1 and subjects in Part 2.

Part 2 – Rifampin (CYP3A4 Inducer and P-gp Inhibitor)

In Part 2, the effects of multiple oral doses of rifampin (a strong CYP3A4 inducer) on the PK of LOXO-305 will be investigated. Rifampin, administered as multiple doses, has been selected as a CYP3A4 inducer for this study, in accordance with recommendations in the FDA Guidance for Drug Interaction Studies.⁶

In addition, the effects of single oral doses of rifampin on the PK of LOXO-305 will be investigated. Rifampin has been shown to be an effective inhibitor of P-gp in the gut when administered as an acute single dose. As such, on Day 8, a single dose of rifampin and LOXO-305 will be co-administered to evaluate the effect of P-gp inhibition on the PK of LOXO-305. Once daily dosing of rifampin from Days 8 to 23 will be adequate to attain maximal CYP3A4 enzyme induction.⁹ In Part 2, all study drugs will be administered in the fasted state (ie, following a fast of at least 10 hours prior to and 4 hours after dosing when co-administered with LOXO-305, and a fast of at least 8 hours prior to and 2 hours after dosing when rifampin is administered alone in Part 2, as absorption of rifampin is reduced when administered with food).⁸

3.3. Selection of Doses in the Study

LOXO-305

Single oral doses of 200 mg LOXO-305 on Days 1 and 12 in Part 1, and Days 1, 8, and 17 in Part 2 will be evaluated as this is the anticipated therapeutic dose level. The selected dose level is a conservative safe dose when an increase in exposure is anticipated in the presence of CYP3A4 inhibitor or inducer and P-gp inhibitor, and will meet the objectives of the study. Doses of LOXO-305 from 25 mg QD to 200 mg QD have been evaluated in a Phase 1/2 first-in-human study in patients with previously treated chronic CLL/SLL or NHL with ongoing dose escalation above 200 mg QD as approved by the study's Safety Review Committee. The available data demonstrate that LOXO-305 appears safe and well tolerated at these doses. At all evaluated doses, including doses above 200 mg QD, no dose-limiting toxicities have been identified in humans.¹

Itraconazole

The clinical dose of itraconazole is 200 mg administered once BID and then QD. In this study, itraconazole will be dosed BID for 1 day (Day 8) and then QD for 10 days (ie, Days 9 to 18), with LOXO-305 co-administered on the fifth day after the start of itraconazole dosing

(ie, Day 12). Although itraconazole reaches steady-state at approximately 15 days QD dosing, BID dosing on Day 8 (ie, a loading dose on the first day of dosing) helps to achieve steady-state within 5 days of dosing, allowing co-administration of LOXO-305 and itraconazole on Day 12. Similar dosing schemes have been used in previously reported DDI studies and have demonstrated sufficient inhibition of CYP3A enzymes with 5 days of QD dosing.¹⁰ To maintain the same level of inhibition, itraconazole will be administered until Day 18.

As itraconazole capsules should be administered with a full meal to maximize its absorption, on Days 9 to 11 and 13 to 18, the dose of itraconazole will be administered alone at the actual time of the Day 1 LOXO-305 dose (\pm 1 hour), approximately 30 minutes after the start of a standard breakfast to maximize the inhibition potential. On Day 8, when itraconazole is administered BID, the morning dose will be administered alone at the actual time of the Day 1 LOXO-305 dose (\pm 1 hour), approximately 30 minutes after starting a standard breakfast, and the evening dose will be administered approximately 10 (\pm 1) hours after the morning dose, approximately 30 minutes after starting a standard evening meal. All meals should be entirely consumed within 30 minutes. On Day 12, to assess the DDI under the most sensitive conditions, both itraconazole and LOXO-305 will be administered in the fasted state (ie, following a fast of at least 10 hours prior to and 4 hours after dosing with itraconazole and LOXO-305).

Rifampin

The dose of rifampin selected for this study is 600 mg QD, which is the commonly used clinical dose level. Rifampin will be dosed QD for 16 days (ie, Days 8 to 23), with LOXO-305 co-administered on the first and tenth day after the start of rifampin dosing (ie, Days 8 and 17, respectively). As per literature, an acute dose of rifampin inhibits P-gp-mediated transport while chronic dosing strongly induces CYP3A enzymes and P-gp.¹¹ Therefore, the acute (transporter) effect of a single dose of rifampin on the single-dose PK of LOXO-305 will be assessed to maximize the ability to observe small differences in PK. Sampling up to 24 hours will be sufficient to evaluate the inhibitory effects as P-gp acts mostly in the gut (absorption/distribution phases). Rifampin dosing alone will then be continued QD to assess its induction potential on LOXO-305. The half-life of rifampin is approximately 3 hours following a 600-mg oral dose;⁸ however, the time required to produce maximum enzyme induction is substantially longer for the synthesis of new enzymes. The timeframe from maximum induction by rifampin has been estimated at a minimum of 5 days of 600-mg QD dosing.⁹ In most DDI studies, oral rifampin is typically administered as a 600-mg QD dose for 4 to 18 days.¹² Dosing will continue until Day 23 to maintain induction throughout the PK sampling time.

As absorption of rifampin is reduced when administered with food, on Days 8 and 17, a single oral dose of 200 mg LOXO-305 and a single oral dose of 600 mg rifampin will be administered following a fast of at least 10 hours prior to and 4 hours after dosing. On Days 9 to 16 and Days 18 to 23, rifampin will be administered alone following a fast of at least 8 hours prior to and 2 hours after dosing with rifampin.

4. SELECTION OF STUDY POPULATION

4.1. Screening Procedures

The following screening procedures will be performed for all potential subjects at a visit conducted within 28 days of study entry (ie, prior to Check-in [Day -1]):

- 1. Inclusion/exclusion criteria
- 2. Informed consent
- 3. Demographic data
- 4. Medical history (including review of medication[s])
- 5. Height, weight, and body mass index (BMI)
- 6. Complete physical examination (Section 7.2.5)
- 7. 12-lead ECG measured after the subject has been resting in the supine position for at least 10 minutes (Section 7.2.4)
- Vital signs (including oral temperature, respiratory rate, and supine blood pressure [BP] and pulse rate [measured after the subject has been supine for at least 5 minutes]; Section 7.2.3)
- 9. HDYF? inquiry, AE, SAE, and concomitant medication evaluations (Section 7.2.1)
- 10. Clinical laboratory evaluations (Section 7.2.2; clinical chemistry panel [fasted at least 8 hours], coagulation parameters, CK, CBC, and UA; Appendix 2)
- 11. Screens for hepatitis C virus (HCV) antibody, hepatitis B surface antigen (HBsAg), and human immunodeficiency virus (HIV) antibody (Appendix 2)
- 12. Hemoglobin A1c (HbA1c) test (Appendix 2)
- 13. Screen for selected drugs of abuse, including cotinine and an alcohol breath test (Appendix 2)
- 14. Serum pregnancy test (for female subjects only; Appendix 2)
- 15. Follicle-stimulating hormone (FSH) test (for post-menopausal female subjects only; Appendix 2)
- 16. Thyroid-stimulating hormone (TSH) test (Appendix 2)

4.2. Check-in Procedures (Day -1)

At Check-in (Day -1), subjects will report to the CRU and the following procedures will be performed:

- 1. Review of inclusion/exclusion criteria
- 2. Interim medical history, including concomitant medication(s)
- 3. Weight and BMI
- 4. Abbreviated physical examination (Section 7.2.5)

- 5. 12-lead ECG measured after the subject has been resting in the supine position for at least 10 minutes (Section 7.2.4)
- 6. Vital signs (including oral temperature, respiratory rate, and supine BP and pulse rate [measured after the subject has been supine for at least 5 minutes]; Section 7.2.3)
- 7. HDYF? inquiry, AE, SAE, and concomitant medication evaluations (Section 7.2.1)
- 8. Clinical laboratory evaluations (Section 7.2.2; clinical chemistry panel [fasted at least 8 hours], coagulation parameters, CK, CBC, and UA; Appendix 2)
- 9. Screen for selected drugs of abuse, including cotinine and an alcohol breath test (Appendix 2)
- 10. Serum pregnancy test (for female subjects only; Appendix 2)
- 11. Compliance with concomitant medications and exclusionary restrictions (Section 6)

For subjects to continue their participation in the study, the inclusion/exclusion criteria must continue to be met at Day -1 (as appropriate; #1, Section 4.2). In addition, continued compliance with concomitant medication and other restrictions will be verified.

The Sponsor will review medical history and all screening evaluations for potential subjects prior to enrollment. Prior to dosing, the Sponsor will provide approval of subjects selected for enrollment by the Investigator (or designee).

Subjects who meet all the inclusion criteria and for whom none of the exclusion criteria apply will be eligible to be enrolled into the study. Safety evaluations may be repeated at the discretion of the Investigator (or designee) or Sponsor.

4.3. Inclusion Criteria

Subjects who meet the following criteria at Screening and Check-in (Day -1), unless otherwise specified, may be included in the study:

- 1. Males, and females of non-childbearing potential, between 18 and 55 years of age, inclusive, at Screening.
- 2. Within BMI range 18.0 to 32.0 kg/m^2 , inclusive.
- 3. In good health, determined by no clinically significant findings from medical history, physical examination, 12-lead ECG, vital signs measurements, or clinical laboratory evaluations (Appendix 4) at Screening and/or Check-in (Day -1) as assessed by the Investigator (or designee).
- 4. Female subjects of non-childbearing potential, defined as being permanently sterile (ie, due to hysterectomy, bilateral tubal ligation, bilateral salpingectomy, bilateral oophorectomy, or confirmed tubal occlusion more than 6 months prior to study drug administration) or post-menopausal (defined as at least 12 months post-cessation of menses without an alternative medical cause). Post-menopausal status will be confirmed with a screening serum FSH level ≥ 40 mIU/mL. All female subjects must have a negative qualitative serum pregnancy test (serum human chorionic gonadotropin; serum quantitative human chorionic gonadotropin tests may be used for confirmation as needed) at Screening and Check-in (Day -1).

- 5. Male subjects who are capable of fathering a child must agree to use 1 of the following methods of contraception from the time of the dose administration through 6 months after the last dose of LOXO-305 administration:
 - Male sterilization, with documented confirmation of surgical success. Male subjects will be surgically sterile for at least 90 days prior to Check-in (Day -1). If documentation is not available, male subjects must follow 1 of the contraception methods below:
 - i. Male condom with spermicide, or
 - ii. A male subject must ensure that their female partner meets 1 of the following criteria:
 - intrauterine device (IUD) (hormonal IUD; eg, Mirena[®]). Copper IUDs are acceptable (eg, ParaGard[®]);
 - 2. established use of oral, implanted, transdermal, intravaginal, or hormonal method of contraception associated with inhibition of ovulation; or
 - 3. bilateral tubal ligation; or
 - 4. be post-menopausal with amenorrhea for at least 1 year prior to dosing and FSH serum levels consistent with post-menopausal status.

Male subjects who practice true abstinence because of a lifestyle choice (ie, do not become abstinent just for the purpose of study participation) are exempt from contraceptive requirements. Periodic abstinence by a female partner (eg, calendar, ovulation, symptothermal, post-ovulation methods) and withdrawal are not acceptable methods of contraception. If a male subject is abstinent at the time of signing the ICF but becomes sexually active through EOS, he must agree to use contraception as described above.

For male subjects, sexual intercourse with female partners who are pregnant, or breastfeeding should be avoided. Male subjects are required to refrain from donation of sperm from Check-in (Day -1) until 6 months after administration of study drug.

For subjects who are exclusively in same-sex relationships, contraceptive requirements do not apply.

- 6. Able to understand and provide written informed consent.
- 7. Able to comply with all study procedures, including the 19-night stay for subjects participating in Part 1 or 24-night stay for subjects participating in Part 2 at the CRU and follow-up phone call.

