- Days 9 to 16 and Days 18 to 23 (Period 2): QD oral doses of 600 mg rifampin administered at the actual time of the Day 1 LOXO-305 dose (± 1 hour) following a fast of at least 8 hours prior to and 2 hours after the rifampin dose.

All study drugs will be administered with approximately 240 mL of water. An additional 100 mL of water may be administered if needed.

In Part 1, there will be a washout period of 7 days between the dose of LOXO-305 on Day 1 (Period 1) and the first dose of itraconazole on Day 8 (Period 2).

In Part 2, there will be a washout period of 7 days between the dose of LOXO-305 on Day 1 (Period 1) and the first dose of rifampin and dose of LOXO-305 on Day 8 (Period 2).

Duration of Subject Participation in the Study:

Planned Study Conduct Duration: approximately 90 days.

Screening Period:

Planned Enrollment/Screening Duration: up to 28 days (Day -29 to Day -2).

Length of Confinement:

Part 1: a total of 20 days (19 nights), from the time of Check-in (Day -1) through the 168-hour (post-Day 12) PK blood draw and EOT assessments (Day 19).

Part 2: a total of 25 days (24 nights), from the time of Check-in (Day -1) through the 168-hour (post-Day 17) PK blood draw and EOT assessments (Day 24).

Follow-up Phone Call (End of Study [EOS]): 7 days (± 2 days) after EOT or ET.

Criteria for Evaluation:

Pharmacokinetics:

In Part 1, serial PK blood samples for the analysis of plasma concentrations of LOXO-305 will be collected from predose through 168 hours postdose following administration of LOXO-305 alone on Day 1 (Period 1) and with itraconazole on Day 12 (Period 2). In Part 2, serial PK blood samples for the analysis of plasma concentrations of LOXO-305 will be collected from predose through 24 hours postdose following administration of LOXO-305 and rifampin on Day 8 (Period 2) and from predose through 168 hours postdose following administration of LOXO-305 alone on Day 1 (Period 1) and with rifampin on Day 17 (Period 2).

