Male subjects will be instructed to notify the Investigator immediately if they discover their sexual partner is pregnant. In this instance, the partner must provide written consent before pregnancy information can be collected. When a Clinical Research Unit (CRU) becomes aware that the female partner of a male subject is pregnant, they are to contact the Investigator immediately (within 24 hours of the CRU staff becoming aware of the event) in addition to notifying Covance or the Sponsor's Clinical Safety Representative via email.

All pregnancies should be recorded on the AE electronic Case Report Form (eCRF; as appropriate), in addition to completion of the required pregnancy forms. If the Investigator suspects that a pregnancy was the result of an interaction between the study treatment and the contraceptive method, in addition to the pregnancy the drug interaction should also be captured as a separate AE.

Definition of Serious Adverse Events

An SAE (by Food and Drug Administration [FDA] definition) is any adverse drug experience occurring at any dose that results in any of the following outcomes:

- Death;
- A life-threatening adverse drug experience (ie, one that places the subject, in the view of the Investigator [or designee], at immediate risk of death);
- Inpatient hospitalization or prolongation of existing hospitalization;
- A persistent or significant disability/incapacity;
- A congenital anomaly/birth defect;
- An important medical event that may require medical or surgical intervention to prevent one of the above outcomes.

Important medical events that may not result in death, be life-threatening, or require hospitalization may be considered SAEs when, based on appropriate medical judgment, they may jeopardize the patient or subject and may require medical or surgical intervention to prevent one of the outcomes listed in this definition.

Unexpected Adverse Drug Reaction

An AE or suspected adverse drug reaction is considered 'unexpected' if the event is not listed in the Reference Safety Information section of the Investigator's Brochure (IB) or if it is not listed at the specificity or severity that has been observed for an unapproved investigational medicinal product (IMP).

Reporting

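### The clause returning lifestyle-abstinent men to contraception stops at EOS, although the protocol's contraception period runs 6 months after the last LOXO-305 dose

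*Protocol*

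**What the plan says.** Protocol Section 4.3, criterion 5, requires men capable of fathering a child to use one of the listed "methods of contraception from the time of the dose administration through 6 months after the last dose of LOXO-305 administration". Men who practise true abstinence as a lifestyle choice "are exempt from contraceptive requirements". One sentence qualifies that exemption: a man abstinent at consent who "becomes sexually active through EOS, he must agree to use contraception as described above".

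EOS is a phone call. The Synopsis, under Duration of Subject Participation, gives its timing: "Follow-up Phone Call (End of Study [EOS]): 7 days (± 2 days) after EOT or ET". The notes to the Appendix 4 schedules define EOS in the same way.

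Two other rules concern male subjects. Criterion 5 also states: "Male subjects are required to refrain from donation of sperm from Check-in (Day -1) until 6 months after administration of study drug". That ban has no exception for abstinence. Appendix 1 (Pregnancy) adds: "Male subjects will be instructed to notify the Investigator immediately if they discover their sexual partner is pregnant".

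Criterion 5 separately exempts men exclusively in same-sex relationships. That exemption is not at issue here.

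**The concern.** The duty and the clause that restores it have different end points. The duty lasts 6 months from the last LOXO-305 dose, while the clause responds only to a change in behaviour up to the follow-up call. Nothing in the protocol or SAP expressly addresses an exempt man whose behaviour changes after the call but inside the 6 months.

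Completers are confined to the unit from Check-in to EOT. After dosing, the only time a completer is at home with the clause still open is therefore the 5 to 9 days between discharge and the call. The clause lapses just as he returns to ordinary life.

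At stake is the protection of a partner from a possible exposure that the protocol itself judged to need a 6-month precaution. A man reading the text could reasonably conclude that a change after the call requires nothing of him. No PK result depends on it.

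**Working it through.** The plan states no figure for this interval, so it has to be derived from the schedule.

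**Inputs**
- Last LOXO-305 dose: Day 12 in Part 1, Day 17 in Part 2 (Protocol Section 3.3).
- EOT: Day 19 in Part 1, Day 24 in Part 2 (Protocol Sections 3.1.1 and 3.1.2).
- EOS: 7 ± 2 days after EOT or ET, so 5 to 9 days after (Synopsis; Appendix 4 notes).
- Contraception period: 6 months after the last LOXO-305 dose (Section 4.3). Assumption: 6 calendar months are 181 to 184 days, depending on the start date.

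**Completers: days from last dose to EOS = EOT day + (5 to 9) − last-dose day**

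| | EOS | Days after last dose |
|---|---|---|
| Part 1 | 19 + 5 to 19 + 9 = Day 24 to 28 | 24 − 12 to 28 − 12 = 12 to 16 |
| Part 2 | 24 + 5 to 24 + 9 = Day 29 to 33 | 29 − 17 to 33 − 17 = 12 to 16 |

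**Stretch not expressly covered = 6 months − days from last dose to EOS**
- Shortest: 181 − 16 = 165 days.
- Longest: 184 − 12 = 172 days.
- Share of the 6 months: 165/181 = 91% to 172/184 = 93%.

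**Early terminators.** Assumption: the subject leaves between his last LOXO-305 dose and the next scheduled one.
- Shortest: ET on the dosing day, 0 + 5 = 5 days from last dose to EOS.
- Longest: Part 1, dosed on Day 1 only and leaving by Day 12, (12 − 1) + 9 = 20 days.
- Part 2, dosed on Day 8 and leaving by Day 17: (17 − 8) + 9 = 18 days, inside that range.

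**Reading the clauses together.** If a man becomes active before EOS, the clause points back to the requirement above it, and that requirement carries the full 6 months, so he is covered. If he becomes active after EOS, the clause does not reach him. Whether he is bound then depends on whether the exemption lapses by itself, and the text does not say.

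**The case against.** The strongest reply is that the general rule already covers this man. It binds every man who can father a child, and the exemption describes men who practise abstinence, in the present tense. Once a man stops, he no longer meets its condition and the 6-month duty applies again. On this view the EOS limit can still have a purpose: the man must agree to use contraception, and EOS is the last scheduled contact at which the site can obtain that agreement.

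This is a possible reading, and it is why the text is ambiguous rather than plainly wrong. But it rests on a purpose the protocol never states, and it asks the reader to look past an explicit end point. An operative safety rule should not depend on that.

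The other safeguards help only in part. The sperm-donation ban does not prevent conception through intercourse. Reporting a partner's pregnancy, which Appendix 1 asks for up to 90 days after study drug, acts only after conception. The 6-month ban and the 90-day reporting window do show that the protocol does not otherwise treat EOS as the end of its reproductive precautions.

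Two limits stand in full. The consent form was not available and may state the duty clearly. The number of men concerned is probably very small: they must be fertile, abstinent by lifestyle, and change behaviour within about five and a half months, in a study of 24 subjects of both sexes.

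**Conclusion.** The concern holds as a gap in an operative safety rule. The mismatch of end points is certain from the text. Whether any subject would be misled is not, because that depends on the unseen consent wording and on how many men are exempt, which the documents do not give. The 165 to 172 days measure the length of a window, not a risk. The correction should be made, but it is not critical: neither the PK comparisons nor the sample size is affected.

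**What to change.** In the abstinence sentence of criterion 5, replace the EOS limit with *at any time through 6 months after the last dose of LOXO-305*, and leave the rest of the sentence unchanged. The trigger and the duty then end together, and early terminators are covered by the same words. Check that the consent form and the counselling at discharge say the same.

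The cost is a few words in a protocol amendment and a check of the consent form and counselling. No visits, tests or subjects are added.
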